12.3. Data Analysis Plan

Statistical analyses will be completed using SAS/STAT[®] software, Version 9.4 of the SAS System for Windows (Cary, NC, USA) by a Biostatistician. All tests will be performed with significance level α =0.05 and using intent-to-treat analysis. Outcomes will be assessed for normality (where appropriate) with the Shapiro-Wilk test. If transformed data is still not normally distributed, then non-parametric analyses will be conducted on these outcomes. LARS (least-angle regression) will be used for the covariate selection methodology. Covariates will include, but may not be limited to, the infant sex, gestational age at delivery as well as and the maternal age, weight at screening, parity, race/ethnicity, and gestational diabetes status. Treatment and BMI category will be included in all models. Intent to treat analysis will be the primary analysis type. Both completers and multiple imputation (Markov chain Monte Carlo method, preferred) may also be performed if there is a large amount (>10%) of missing data. However, we will extract the mothers' WIC record and therefore for participants who fail to return to clinic, weight measurements will be acquired from the planned chart abstraction. This should greatly decrease the amount of missing data from loss to follow-up.

Hypothesis A: Higher incidence rate of appropriate GWG

Initial results will be expressed contingency tables with incidence rate and either treatment or BMI category. Tests for associations between these variables will be based on Pearson's Chi-squared statistic. Further results will be based on a generalized linear mixed effect model with a binary distribution and a log odd link function modeling the incidence rates. The model will use random effects to account for a site effect and within-subject correlation over time. Results from this model will be reported as odds ratios of least square means, with p-values based on z-tests. Two different sets of models will be used. The first set of models will contain only treatment and BMI category, while the second is will also contain the covariates based on LARS. Pairwise post-hoc comparisons of the category variables will be corrected for multiple comparisons will be made when necessary.

Hypothesis B: Small Deviation in Weekly GWG

Overall deviation rates will be reported using a linear effect mixed model, using random effects to account for site and within-subject correlation. The response is the deviation of the weekly GWG rates from the IOM guideline rates. Models will be reported using both the simple model with treatment and BMI category and with covariates selected by LARS. Adjusted means of the deviations will be obtained using the least squared means. Two-sample t-test will be used to compare adjusted mean deviations.

Hypothesis C: Improvements in Physiological and Behavioral Factors

Each physiological and behavioral factor will be investigated independently from each other. Linear mixed effect models, like the ones listed in 2B, will be used to test differences between the treatment groups with least square

means. The response for each of these models will include both repeated measures and percent change from baseline approaches.

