3.1 Distributional assumptions

Preliminary statistical testing will be performed to investigate homoscedasticity and normality of model residuals. Visual inspections will initially be performed, followed by more tests when departures from normality are present.

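### For the Hypothesis C outcomes that the SAP does not cover, a Shapiro-Wilk test on the outcome can replace the planned mixed model with an unnamed non-parametric analysis; the residual check in SAP 3.1 is a cheap improvement

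*Protocol*

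**What the plan says.** Protocol 12.3 sets one distributional rule ahead of the hypothesis-specific analyses: "Outcomes will be assessed for normality (where appropriate) with the Shapiro-Wilk test". The consequence follows: "If transformed data is still not normally distributed, then non-parametric analyses will be conducted on these outcomes". Neither the transformation nor the non-parametric method is named.

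For Hypothesis C the same section plans a model: "Linear mixed effect models, like the ones listed in 2B, will be used to test differences between the treatment groups". The reference is to the Hypothesis B model, which is described as "using random effects to account for site and within-subject correlation". The section also says: "Treatment and BMI category will be included in all models". Baseline is not in the covariate list. It enters because the response is to be handled both as repeated measures and as percent change.

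SAP 3.1 takes a different approach: "Preliminary statistical testing will be performed to investigate homoscedasticity and normality of model residuals". It starts with visual inspection, adds tests only if departures appear, and contains no switch to non-parametric methods. The SAP's hypotheses (1.3, 4.3), however, cover gestational weight gain, with binary perinatal outcomes as exploratory. Its amendment list records that the secondary-objective section was taken out, and SAP 3.6 limits the planned analysis to pregnancy outcomes. For the remaining Hypothesis C outcomes, Protocol 12.3 still stands.

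**The concern.** Three features of the rule matter together.

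- **Wrong target.** A linear mixed model makes its normality assumption about residuals and random effects, not about the pooled outcome. This trial recruits three BMI categories in roughly equal numbers, so an outcome strongly related to BMI is a mixture and can look non-normal while the model is correct.
- **Dependence on sample size.** The power of Shapiro-Wilk rises with the number of women, while the need for normality when comparing means falls. The rule is strictest where it is least needed.
- **Open fallback.** The planned model carries treatment, BMI category, site and within-subject correlation. The fallback is not required to carry any of them.

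At stake are precision and comparability for the secondary outcomes. An adequate model could be dropped outcome by outcome on a p-value. Some outcomes would then be reported as mean differences and others by a rank test without an estimate on the outcome's own scale.

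**Working it through.** **Sample size.** The documents give no figure for Hypothesis C or for the normality test, so the starting point is the number of women analysed. The plan's totals reproduce with the usual two-proportion formula (pooled variance, two-sided α = 0.05 assumed, power 0.80, no continuity correction), n per arm = [1.960·√(2p̄q̄) + 0.842·√(p₁q₁ + p₂q₂)]² / (p₁ − p₂)²:

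- 28.7% vs 42.7%: 183 per arm, 366 in all, 366/0.85 = 431 (protocol: 432).
- 28.7% vs 44.7%: 142 per arm, 284 in all, 284/0.85 = 335 (SAP: at least 330).

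After 15% attrition the analysed numbers are 330 × 0.85 ≈ 280 and 432 × 0.85 ≈ 367. Applying 15% to these outcomes is an assumption.

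**How often the test rejects.** The level is the protocol's: "All tests will be performed with significance level α =0.05 and using intent-to-treat analysis". The documents give no outcome distributions, so every shape below is an assumption (2,000 simulated data sets per cell).

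| Outcome shape | n = 30 | n = 280 | n = 367 |
|---|---|---|---|
| Exactly normal | 4% | 5% | 5% |
| Skewness 0.5, untransformed | 14% | 86% | 94% |
| Skewness 1, untransformed | 43% | 100% | 100% |
| Skewness 1, after log | 15% | 86% | 95% |
| Skewness 1, after square root | 8% | 38% | 47% |
| Skewness 1, after cube root | 5% | 5% | 5% |
| Zero-heavy count, after log(1+x) | 42% | 100% | 100% |
| Normal residuals, BMI means 0.5 SD apart | 6% | 4% | 5% |
| Normal residuals, BMI means 1 SD apart | 4% | 7% | 8% |
| Normal residuals, BMI means 2 SD apart | 9% | 91% | 98% |

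Floor-type scores at n = 280 failed untransformed and after log, square root and cube root in 100% of runs.

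**Whether rejection means that the mean comparison is unsafe.** For skewness 1 and for the zero-heavy count, a plain t-test with 140 or 184 women per arm had type I error between 0.044 and 0.052. A rejection at this size therefore does not by itself discredit a comparison of means.

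**What a fallback without BMI category could cost.** Assume absolute body weight that is exactly normal within BMI category, means 60, 73 and 93 kg, SDs 7, 8 and 11 kg, equal categories, 140 women per arm and a true difference of 3 kg. Such data failed Shapiro-Wilk raw in 100% of runs and after log in about 81%, although the model is correct.

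- Within-category variance: (49 + 64 + 121)/3 = 78.
- Between-category variance: mean 75.33, (15.33² + 2.33² + 17.67²)/3 = 184.2. Total: 262.2.
- Adjusted for BMI category: SE = √(2 × 78/140) = 1.056; power = Φ(3/1.056 − 1.960) = Φ(0.88) = 81%.
- Unadjusted, BMI balanced only by chance: SE = √(2 × 262.2/140) = 1.935; power = Φ(3/1.935 − 1.960) = Φ(−0.41) = 34%.
- Unadjusted, BMI balanced by stratified randomization: the test still uses 1.935, but the difference varies with SE 1.056. The threshold is 1.960 × 1.935 = 3.793; power = Φ((3 − 3.793)/1.056) = Φ(−0.75) = 23%. Type I error is 2Φ(−3.793/1.056) ≈ 0.0003.

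Simulation agrees: about 80% for the BMI-adjusted linear model, against 32% to 33% (chance balance) and 20% to 23% (stratified balance) for a Wilcoxon rank-sum test. The arithmetic for the unadjusted mean comparison gives almost the same loss, so the loss comes from dropping BMI category and not from ranking.

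**The case against.** A reader might infer that a test on the raw outcome decides, that most behavioral outcomes would be switched, and that they would lose BMI, site, baseline and repeated-measures structure. The documents do not support this.

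- **Raw outcome.** The deciding test is on transformed data, and the check applies only where judged appropriate, which leaves discretion.
- **Most outcomes.** With no distributions and no named transformation, the rejection rate after transformation runs from about 5% to 100%. A skewness-1 outcome that usually fails after log usually passes after a cube root.
- **BMI mixture.** It matters only under strong separation: at 0.5 to 1 SD the rejection rate stays at 4% to 8% at the trial's size. The listed postpartum endpoint is weight retention, a change. With assumed category means of 3, 4 and 2 kg and SD 5 kg it was rejected in about 5% of runs. The absolute-weight example shows a mechanism, not an expected frequency.
- **Loss of structure.** It is permitted, not stated. Rank-based models can carry BMI category and repeated measures, and the sentence placing BMI category in every model may be read as covering the fallback.
- **Baseline.** It is not a listed covariate, so no loss of baseline adjustment can be charged to the switch.

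It is also fair that these outcomes are secondary, that SAP 3 asks for cautious reporting of secondary results as point estimates with 95% confidence intervals, and that a later plan for these outcomes is possible.

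All of this limits the size of the point. It does not remove the rule: a test of the outcome still triggers a change of method, the method is still unnamed, and the sponsor's own SAP uses a different check.

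**Conclusion.** The point holds as a cheap improvement to the plan for secondary outcomes. For the Hypothesis C outcomes outside the SAP, Protocol 12.3 tests the wrong quantity, at a sample size where the test detects harmless departures, and leads to a fallback that need not keep the design terms. Floor-type scores are the clearest case, because no usual transformation rescued them.

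The possible cost is large only if two things coincide: the outcome is strongly related to BMI category and the fallback is an ordinary two-sample rank test. Under the assumed weight values, power then falls from about 80% to 32% or lower. That figure illustrates the risk and does not forecast any named endpoint. The number of outcomes affected cannot be derived from the documents. The gestational weight gain analyses in the SAP are not affected, because SAP 3.1 has no such switch.

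**What to change.** Add one paragraph to the SAP, or amend Protocol 12.3, for the Hypothesis C outcomes:

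- Delete the Shapiro-Wilk rule and the switch to non-parametric analysis.
- Apply the SAP 3.1 check to model residuals, visual inspection first.
- Keep the planned linear mixed model as the analysis, with treatment, BMI category and the site and subject random effects.
- Use robust (sandwich) or bootstrap standard errors where residuals are clearly skewed.
- Show rank-based results as sensitivity only, by a named method that keeps BMI category.

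This needs no new data and brings the protocol into line with the SAP. The one small downside is that mean differences on very skewed scores need careful wording.

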2.1. Hypotheses

Relative to WIC participants receiving Usual Care, participants receiving SmartMoms® will have a:

A: higher incidence of appropriate GWG according to the 2009 IOM guidelines

B: smaller deviation in GWG per week from the 2009 IOM guidelines

C: significant improvements in both physiological and behavioral factors including diet quality, physical activity, birth outcomes, postpartum weight loss, quality of life and mood and WIC food voucher redemption rates.

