2.2. Endpoints

Primary endpoint:

• Incidence of appropriate weight gain in pregnancy as defined by the 2009 IOM Guidelines [2].

Secondary endpoints:

- Rate of GWG per week
- Maternal diet (24h recall)
- Physical activity (Accelerometry, Pregnancy Physical Activity Questionnaire)
- Quality of life and stress (Depression Anxiety Stress Scales-21, Quality of Life Inventory, Household Chaos Questionnaire)
- Maternal and infant birth outcomes
- Infant feeding style (Infant Feeding Style questionnaire and Breastfeeding Questionnaire)
- WIC food voucher redemption rate
- Postpartum weight retention (measured 1, 6 and 12 months after delivery)

Exploratory endpoints: This study is also powered for a comparison of GWG between BMI categories. As an exploratory aim we will test whether maternal body mass index (BMI) is a moderator of intervention effects on GWG (relative to Usual Care).

Planned post-hoc analyses include testing moderators of intervention effects on GWG in BMI categories, race/ethnicity groups and in the SmartMoms[®] group only, intervention adherence.

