9.2. Visits 2-6

At each visit, participants will have their weight, percent body fat, and blood pressure measured.

At V3, V4, V5, and V6, questionnaires will also be administered. At V3, V5, and V6, diet (24h dietary recall) and physical activity (accelerometry) will be administered to participants to be completed over the next 5-7 days. At the end of pregnancy and at 12 months postpartum, the WIC chart will be abstracted. After delivery, the birth certificate (long form) which captures birth and prenatal outcomes will be obtained.

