covariates. Variable section is now a priori, no variable section methods are needed. This section has been removed

Section 3.4 – removed now

Amendment May 2024:

Mediation and moderator section has been removed since these are intended to be exploratory analyses

Section 3.4

Amendment May 2024:

No missing data will be imputed, and the missing data section is adjusted accordingly. Data is missing not at random (MNAR) for participants that have early deliveries, and a sensitivity analysis will be conducted to include data from the visit during mid-pregnancy for individuals that had missing data at the late pregnancy visit time point. See section 4.1 for more details.

Section 3.6 – removed now

Amendment May 2024:

Details about how tables and figures will be expressed in tables have been removed to not limit how results can be presented in order to comply with journal guidelines.

Section 4.0

Amendment May 2024:

The description of the analysis was moved to this section as it was originally written for each individual hypothesis. There are no changes in analysis, but details were moved from this general analysis section to remove repetitive sections of the analysis descriptions.

Section 4.1

Amendment May 2024:

To better match the wording of the analysis that will be used, the details of intent-to-treat analysis approaches, including description of the included analysis populations were spelled out.

Section 4.2

Amendment May 2024:

Each of the study outcomes are explicitly defined to provide transparency and clarity on exact definitions.

Section 4.3.1 – now removed

Amendment May 2024:

Hypothesis analysis description was reduced since a general description of the analysis is written in section 4. No changes are made to the actual analysis.

Section 4.4 – now removed

Amendment May 2024:

Removed the secondary objective section since it is not part of the primary results.

Section 4.5 – now removed

Amendment May 2024:

Removed the mediator and moderator section since it is not part of the primary results.

Statistical Analysis Plan Prepared by [name] (Biostatistician)

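### Hypothesis C outcomes not re-specified in the SAP are to be analysed both as repeated measures and as percent change from baseline, with neither named as the lead and no rule for zero or absent baselines

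*Protocol*

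**What the plan says.** Protocol 2.1, Hypothesis C, expects "significant improvements in both physiological and behavioral factors including diet quality, physical activity, birth outcomes, postpartum weight loss, quality of life and mood", together with WIC voucher redemption. Protocol 2.2 lists the matching secondary endpoints, among them "Quality of life and stress (Depression Anxiety Stress Scales-21, Quality of Life Inventory, Household Chaos Questionnaire", and adds infant feeding style.

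Protocol 12.3 gives the analysis. The sentence on the model begins "Linear mixed effect models, like the ones listed in 2B, will be used to test differences between the treatment groups with least square". The sentence after it reads: "The response for each of these models will include both repeated measures and percent change from baseline approaches". Nothing says which response gives the reported answer, or what happens when a baseline is zero or absent. The covariate list, which opens "Covariates will include, but may not be limited to, the infant sex, gestational age at delivery as well as and the maternal age, weight", does not name the outcome's own baseline value, although the list is open-ended. The same section commits to "All tests will be performed with significance level α =0.05 and using intent-to-treat analysis".

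The SAP amendment entry for its Section 4.4 reads: "Removed the secondary objective section since it is not part of the primary results". SAP 4.3 then gives models only for gestational weight gain and, as exploratory, for adverse perinatal outcomes. SAP 3.3 fixes the covariates as gestational age at randomization, BMI category and parity. Percent change is not mentioned in the SAP.

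**The concern.** There are three difficulties, and only the third depends on numerical assumptions.

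1. **The response is not always defined.** Percent change is (follow-up − baseline)/baseline, so a woman with a zero baseline has no value. She would leave one of the two planned analyses and stay in the other, which sits badly with the intent-to-treat commitment. Some outcomes have no baseline at all.
2. **There are two unranked answers per outcome.** Each factor is tested by two responses, and SAP 3 applies no multiplicity adjustment to secondary outcomes. When the two disagree, the plan does not say which result stands.
3. **Power and interpretation suffer.** Dividing by a variable baseline adds noise and skew. If one woman goes from 2 to 4 (+100%) and another from 4 to 2 (−50%), the mean percent change is +25% although the mean score has not moved.

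At stake is the precision and credibility of the secondary results, not the primary comparison.

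**Working it through.** **What the plan gives.** No SD, correlation, effect size or power is stated for any Hypothesis C outcome, so there is no figure to reproduce for this point. Only the sample size carries over. It was set for the primary outcome: 28.7% versus 42.7%, two-sided 0.05 and 80% power give 183 per arm, and 366/0.85 = 431, against the stated 432. The current target is at least 330. After 15% attrition, 330 × 0.85 = 280.5, or about 140 per arm.

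**Assumptions.** One baseline and one follow-up, normal outcome, true effect 0.30 SD, two-sided 0.05, baseline/follow-up correlation r of 0.3, 0.5 or 0.7, and baseline coefficient of variation (CV) of 10%, 20% or 30%.

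**Closed form.** For effect d in SD units and n per arm, power ≈ Φ(d/SE − 1.96), with √(2/140) = 0.1195 and 0.30/0.1195 = 2.510.
- Baseline-adjusted: SE = √(2/n) × √(1 − r²). The ratios d/SE are 2.510/0.954 = 2.63, 2.510/0.866 = 2.90 and 2.510/0.714 = 3.51. Power is about 75%, 83% and 94%.
- Simple change, which stands in for the group-by-time contrast of a repeated-measures model: SE = √(2/n) × √(2(1 − r)). The ratios are 2.510/1.183 = 2.12, 2.510/1.000 = 2.51 and 2.510/0.775 = 3.24. Power is about 56%, 71% and 90%.

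**Simulation.** Percent change has no simple closed form. Simulated ranges over r = 0.3 to 0.7:

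| Analysis | Power |
|---|---|
| Baseline-adjusted | 73–94% |
| Simple change | 55–90% |
| Percent change, CV 10% | 55–88% |
| Percent change, CV 20% | 48–86% |
| Percent change, CV 30% | 27–62% |

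The last row is unstable because a few baselines fall near zero. Other runs of the same scenario gave up to 34–70%, still well below simple change.

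**Skewed outcomes.** With lognormal data and the effect set for about 80% adjusted power under normality, a proportional effect gave 51–73% for percent change against 71–78% for the adjusted model. With an additive effect, percent change gave 62–89% against 77–80%. It was ahead at correlation 0.7 with CV of 40% or more.

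**Two answers.** Across scenarios with a true effect, percent change and the change contrast disagreed on significance in about 3–43% of simulated trials. Under the null with skewed baselines, taking whichever was significant raised the per-outcome false-positive rate from 5% to about 6–8%.

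**Zero baselines.** Suppose 80% power with all women and a share f dropped. Then power = Φ(2.80 × √(1 − f) − 1.96). For f = 5%, 10%, 20% and 30% this is 78%, 76%, 71% and 65%. The documents give neither f nor the scoring ranges, so this only shows the scale of the loss.

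**Outcomes without a baseline.** Protocol Table 3 schedules diet recall and accelerometry at screening, and weight and questionnaires at Visit 1, so most outcomes have a baseline. Protocol 10.4 places the Breastfeeding Questionnaire only postpartum. WIC abstraction is scheduled at late pregnancy and 12 months, so a baseline redemption rate may not be captured. Birth outcomes arise later still: "After delivery, the birth certificate (long form) which captures birth and prenatal outcomes will be obtained".

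**The case against.** Several points on the other side stand.

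- A reader might infer that the SAP drops every Hypothesis C outcome. It does not: SAP 4.2 and 4.3 define adverse perinatal outcomes and give them one logistic model. The protocol sentence no longer governs those.
- A reader might charge the whole gap between baseline adjustment and percent change to percent change. Part of it comes from not adjusting for baseline, which the planned repeated-measures contrast may share. Against simple change, percent change costs only about 1–7 points at CV 10–20%; the large gap appears at CV 30%.
- A reader might infer that percent change always loses power, or that a large share of women would be excluded for zero baselines. Neither is supported. Some skewed settings favour percent change, and no share of zeros is documented. Zero is plausible for a symptom score, less so for activity minutes averaged over days with more than 8 hours of awake wear (protocol 10.3), and impossible for body weight. Women with a zero baseline also remain in the repeated-measures analysis.
- Protocol 12.3 already provides for transformation and then non-parametric analysis. That deals with skew, but it neither defines a division by zero nor says which response leads.
- SAP 3 names linear and linear mixed models as its main methodology and says secondary results should not be read as definitive. This lowers the stakes without choosing between the two responses.

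**Conclusion.** The point holds for the Hypothesis C outcomes that the SAP leaves to the protocol: diet, physical activity, mood and quality of life, infant feeding, voucher redemption and postpartum weight. For these, two responses are planned with no lead, and one of them cannot be formed for a zero or absent baseline. That follows from the text alone.

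The power loss is usual rather than universal. Its size, from a few points to more than 40, depends on an assumed CV, correlation, effect and distribution, and should be quoted only as a range. A reader might go further and infer that the primary result is compromised; nothing in the documents supports that, since the weight-gain outcomes have their own models in SAP 4.3. Severity is low to moderate.

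**What to change.** Revise the Hypothesis C text in protocol 12.3, or restore a short secondary-outcome section in the SAP, before these outcomes are compared by arm:

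1. Remove percent change as an inferential response. If it is wanted for readers, label it descriptive and give the number of women for whom it cannot be computed.
2. Name one analysis per outcome: follow-up values in the mixed model with the outcome's own baseline as a covariate, or a constrained-baseline longitudinal model. State the visit at which the arms are compared.
3. For skewed outcomes, use a transformation defined at zero (a plain logarithm is not) or the non-parametric route already in 12.3.
4. For outcomes with no baseline, such as breastfeeding, and voucher redemption if no baseline is abstracted, compare the arms without a baseline term.
5. State that birth outcomes follow the logistic model in SAP 4.3.

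The cost is about a paragraph of text. It needs no new data, because the baselines used are already scheduled at screening or Visit 1.
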